#### 7.5.4.3 Immunogenicity

Serum and CSF samples are collected for central laboratory analysis of SOBI003 ADAs by a validated immunoassay method (York Bioanalytical Solutions Limited, York, UK). Assays are being developed for assessment of neutralizing antibodies, both for antibodies inhibiting cellular uptake and for enzyme activity inhibiting antibodies (BioAgilytix, Hamburg, Germany). At each sampling occasion, a blood volume of 1.5 mL will be collected.

Serum samples are collected prior to start of SOBI003 infusion at Weeks 38, 52, 78 and 104, and during Early Termination. Triplicate aliquots are required for each sampling time point.

CSF samples (0.5 mL) are collected at Weeks 52 and 104.

If the dose of SOBI003 is adjusted in a patient, serum samples are collected prior to start of the first adjusted infusion and then prior to the 3rd adjusted infusion i.e., at 2 occasions per dose adjustment.

For patients with an ADA-positive serum sample, the following will also be determined in serum: ADA titer, IgG subclasses, and presence of NAb.

For patients with an ADA-positive CSF sample, the following will also be determined in CSF: ADA titer and presence of NAb.

Should any patient permanently discontinue SOBI003 treatment, then a serum sample will be collected 30 to 40 days after the last SOBI003 administration for ADA assessment. Should the sample be ADA-positive, then the ADA titer will be determined and ADA samplings will continue at approximately monthly basis until the ADA has disappeared or titers have stabilized at a lower level.

The impact of ADAs on the safety, tolerability, and PK of SOBI003 will be explored, as well as the potential impact on HS levels in CSF, serum and urine.

Sampling details are provided separately in the Study laboratory manual.

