In addition, at each time point a sample is collected for immunogenicity, a blood sample is obtained for determination of SOBI003 in serum. In case of a time deviation for the immunogenicity sample, the time for the PK sample should be adjusted accordingly, or an additional PK sample may have to be collected. Therefore, in case the SOBI003 treatment is terminated prior to Week 104, then a PK and immunogenicity sample should be obtained as soon as possible after the decision of early treatment termination, as well as 30 to 40 days after the final SOBI003 infusion.

For patients with confirmed ADA levels, blood samples for PK and immunogenicity analysis should continue in accordance with Section 7.5.4.3.

CSF samples (0.5 mL) are collected during general anesthesia at Day 2 on Weeks 52 and 104 for determination of SOBI003. Triplicate aliquots are required for each sampling time point. At the time of CSF sample collection, a blood sample will also be collected for determination

of SOBI003 in serum. In case the time point for the CSF sample is deviating from the planned time point, the blood samples should be adjusted accordingly.

The exact time of the SOBI003 infusion start and completion as well as of each PK sampling are recorded in the CRF for each patient.

Sampling, storage and shipment details are provided separately in the Study laboratory manual.

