8.3 PK analysis set

The PK analysis set will consist of those patients in the safety analysis set who have at least one SOBI003 serum concentration value, without any protocol deviation jeopardizing the PK evaluation. For each patient in the study, all the associated safety and efficacy data in the SOBI003-001 study will be pooled and presented together with the SOBI003-002 study.

The PK analysis set will be used for the PK analyses.

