16.1 Pharmacokinetic Parameters

The PK analysis will be based on the PK analysis set.

Serum concentrations will be listed and summarised by time point. Individual serum concentration profiles will be plotted both on the original scale and on the log scale. Mean (\pm SD) and median serum concentration profiles will be plotted for each dose both on the original scale and on the log scale. The individual serum concentration data, and the actual time for IMP administration and blood sampling will be used in the derivation of the PK parameters.

PK calculations, based on serum concentrations, will be performed in Phoenix WinNonlin by means of NCA. The following multiple-dose PK parameters will be determined for SOBI003 at Weeks 39, 52, 78 and 104, and during dose-adjustments:

- The time of the end of the infusion of SOBI003, tEnd of inf
- The observed serum concentration at the end of infusion of SOBI003, CEnd of inf
- The observed serum concentration immediately before the start of infusion of SOBI003, CPre-dose
- The area under the plasma concentration-time curve from time 0 to last sample, AUC168h
- Clearance, CL

AUC168h will be calculated according to the linear log trapezoidal method. Other PK parameters may be calculated as applicable.

In addition to evaluating SOBI003 PK based on SOBI003-002 data only, PK of SOBI003 will also be evaluated based on study SOBI003-002 together with PK data obtained from study SOBI003-001, since administration of SOBI003 have been started in study SOBI003-001 for all patients.

Pre-dose SOBI003 concentrations in study SOBI003-002 will be used to explore if steady-state is maintained or if SOBI003 serum concentrations decrease or increase following totally 2 years administration of SOBI003. The extent of accumulation of SOBI003 serum concentrations during 2 years treatment will be explored by calculating accumulation ratio (Rac) based on PK data from both study SOBI003-001 and study SOBI003-002. Rac will be calculated as $AUC_{0-168h} \text{ week } n / AUC_{0-168h} \text{ week } 1$, where n is 38, 52, 78 and 104.

The ratio of peripheral/central serum concentrations of SOBI003 may be explored in study SOBI003-002, in case SOBI003 serum concentrations have been determined in this study, depending on the outcome of study SOBI003-001.

The effect of eg. dose-level, age or body-weight on SOBI003 PK will be explored eg. by plotting PK parameters versus dose, age, body-weight.

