The PK parameters will be listed for each patient and summarized for each IMP dose using descriptive statistics (the number of patients, arithmetic mean, standard deviation, standard error, coefficient of variation (CV) expressed as a percentage, geometric mean, geometric CV%, median, minimum, maximum). This summary will be repeated for PK parameters within baseline ADA positive and baseline ADA negative subgroups, within ADA positive at any postbaseline visit and ADA negative at all postbaseline visits.

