16.2 Immunogenicity

The analysis of immunogenicity will in general be based on the immunogenicity analysis set. However, exceptions are the analyses of PK by ADA status at baseline, which will be based on the PK analysis set, and the AE analysis with ADA-categorized AEs in section 15.2.1.

For immunogenicity, baseline ADA (pre-existing ADA) from the previous study will be used.

The following definitions will apply as defined in the harmonised terminology for immunogenicity (Shankar et al., 2014, “Assessment and Reporting of the Clinical Immunogenicity of Therapeutic Proteins and Peptides—Harmonized Terminology and Tactical Recommendations”, The AAPS Journal, DoI:10.1208/s12248-014-9599-2):

- Evaluable patient: A patients with at least one sample taken after IMP administration that is appropriate for ADA testing (with reportable result).
- ADA-positive sample: When ADA is detected in a sample, the sample is considered positive.
- Baseline ADA: pre-existing antibodies detected at baseline.
- Treatment induced ADA: de novo development following administration of IMP (i.e., formation of ADA any time after the initial IMP administration in a patient without pre-existing ADA).
- Treatment boosted ADA: Baseline ADA boosted to higher level following IMP administration (i.e., at any time after the initial IMP administration the ADA titer is greater than the baseline titer by a factor of four).
- ADA-positive patient: A patient with at least one treatment-induced or treatment-boostered ADA-positive sample at any time during the treatment or follow-up observation period.
- ADA-negative patient: A patient without a treatment induced or treatment-boostered ADA-positive sample during the treatment or follow-up observation period.
- Baseline ADA Positive Patient: Patient with ADA at baseline. Such patient can have treatment boostered ADA after dosing.

Note that the requirement for inclusion in the immunogenicity set of at least one post-dose ADA assessment means that all patients in the immunogenicity set are “evaluable patients”.

The immunogenicity data will be listed for each patient and individual patient plots of titer measurement over time presented. Titer measurements will be summarized by visit and time point using descriptive statistics by IMP dose and overall. Immunogenicity will be evaluated in regards antibody prevalence (pre-existing antibodies), antibody incidence, titer and boosting following dosing, impact on pharmacokinetics responses.

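### SAP 16.1 groups PK by whether a patient is ever ADA-positive, not by ADA status at the time, which can dilute a descriptive ADA effect; the SAP also omits the ADA-by-HS evaluation the protocol promises

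*SAP*

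**What the plan says.** **PK by ADA status.** SAP 16.1 summarises the PK parameters descriptively for each dose. It repeats that summary by baseline ADA status and "within ADA positive at any postbaseline visit and ADA negative at all postbaseline visits". SAP 16.2 defines an ADA-positive patient in the same whole-study way: "A patient with at least one treatment-induced or treatment-boostered ADA-positive sample at any time during the treatment or follow-up observation period".

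**Which PK data.** SAP 8.3 defines the PK analysis set and adds that "all the associated safety and efficacy data in the SOBI003-001 study will be pooled and presented together with the SOBI003-002 study". SAP 16.1 states that "PK of SOBI003 will also be evaluated based on study SOBI003-002 together with PK data obtained from study SOBI003-001", and uses the Week 1 AUC as the denominator of the accumulation ratio.

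**Sampling.** Protocol 7.5.4.3: "Serum samples are collected prior to start of SOBI003 infusion at Weeks 38, 52, 78 and 104, and during Early Termination". It adds samples around dose adjustments. Protocol 7.5.5.1: "at each time point a sample is collected for immunogenicity, a blood sample is obtained for determination of SOBI003 in serum".

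**ADA and HS.** Protocol 7.5.4.3 says the impact of ADAs on safety, tolerability and PK will be explored, "as well as the potential impact on HS levels in CSF, serum and urine". The synopsis, under statistical methods, names the impact on both PK and PD. The matching sentence in SAP 16.2 reads "antibody incidence, titer and boosting following dosing, impact on pharmacokinetics responses" and goes no further.

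**The concern.** ADA status can change over two years. The plan expects this: time to seroconversion and transient versus persistent response are endpoints. A label fixed by the whole follow-up ignores that. A child who is negative at Weeks 38 and 52 and positive at Week 78 contributes the Week 38 and 52 exposure to the ADA-positive column. A short-lived low titer counts the same as a lasting neutralising response. If antibodies lower exposure, mixing unaffected occasions into the positive group makes the two columns look more alike.

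The SAP uses a better rule elsewhere. SAP 15.2.1 classifies each adverse event by the ADA status when it occurred, and SAP 16.2 uses the nearest previous titer. PK gets neither.

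At stake is whether the report can describe how antibodies relate to exposure. The protocol gives a reason to look: Section 5.1.4 reports that ADAs in cynomolgus monkeys appeared to affect exposure, possibly the AUC. Without an ADA-by-HS display, a weak CSF HS response could not be set against antibody status in any planned output, and CSF HS is the first step of the testing hierarchy.

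**Working it through.** The plan gives no figure for the PK-by-ADA summary, so there is nothing to reproduce. The arithmetic below shows the mechanism only.

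**Formula.** Let R be the true ratio of exposure after seroconversion to exposure without ADA. Let f be the fraction of an ever-positive patient's PK occasions that fall before seroconversion. If pre-conversion exposure equals that of never-positive patients, the geometric-mean ratio of ever-positive to never-positive is R^(1−f). With concurrent classification f = 0, and the summary shows R.

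**Inputs.** The extension PK weeks are 38, 52, 78 and 104 (Protocol 7.5.5.1), so f is 0, 1/4, 2/4 or 3/4. Adding only Week 1 of SOBI003-001 gives five occasions. For a patient without pre-existing ADA, the first-dose occasion precedes any treatment-induced ADA, so f is at least 1/5. R and the conversion times are assumptions.

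| Assumed R | Extension only: 0, 1, 2, 3 of 4 before conversion | With Week 1: 1, 2, 3, 4 of 5 before conversion |
|---|---|---|
| 0.30 | 0.30, 0.41, 0.55, 0.74 | 0.38, 0.49, 0.62, 0.79 |
| 0.50 | 0.50, 0.59, 0.71, 0.84 | 0.57, 0.66, 0.76, 0.87 |
| 0.70 | 0.70, 0.77, 0.84, 0.91 | 0.75, 0.81, 0.87, 0.93 |

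Example: R = 0.50 with two of four occasions before conversion gives 0.50^(1−0.5) = 0.71.

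**Visit by visit.** SAP 16.1 does not say whether the parameter summary pools occasions. If it is read per visit, with an assumed 6 ever-positive patients of whom m have converted by that visit, the ratio is 0.50^(m/6): 0.63, 0.71 and 0.79 for m = 4, 3 and 2.

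**Is concurrent ADA available for each PK value?** Mostly.

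| PK occasion | ADA sample |
|---|---|
| Weeks 38, 52, 78, 104 | Yes, pre-infusion the same week |
| First adjusted infusion | Yes in Protocol 7.5.4.3; Table 8 marks ADA at Week 3 only |
| Third adjusted infusion | Yes |
| Weeks 4 and 8 after a dose adjustment | None (Table 9) |

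Pairing therefore runs from ADA to PK, not the reverse. For the last row the nearest previous scheduled sample is the one before the third adjusted infusion, 4 − 3 = 1 week and 8 − 3 = 5 weeks earlier, unless a scheduled-week sample falls between.

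**HS.** The SAP 14.2 models contain baseline level, age, accumulated dose and sex, with no ADA term. No HS summary by ADA status or titer is listed. Population PK/PD results are reported outside the clinical study report. Protocol 7.5.5.4 gives body weight, age and dose level as example covariates for the population PK model, and neither that section nor 7.5.5.5 names ADA. Serum and urine HS are taken in the same four weeks as serum ADA, and CSF HS at Weeks 52 and 104 with CSF ADA.

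**The case against.** The output is a descriptive summary without a test, in 9-12 children. SAP 16.1 already plans accumulation ratios at Weeks 38, 52, 78 and 104, pre-dose trends, individual concentration plots and per-patient PK listings. SAP 16.2 plans titer plots per patient, and SAP 14.2 plans HS figures by subject. A reader could match these by hand. SAP Section 2 also allows exploratory analyses that it does not list. All this stands, and it limits the consequence. But no planned output puts exposure or HS beside concurrent ADA.

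Several stronger readings might be inferred, and the documents do not support them:

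- **Dilution of known size, always toward no effect.** Conversion timing is not given. The direction assumes that converters and never-positive patients have the same exposure before conversion. Protocol 5.1.4 links ADA development to endogenous enzyme expression, and 7.5.5.2 says the assay may cross-react with endogenous enzyme, so this is not assured.
- **No comparison left if every patient converts.** The ever/never split would then be empty, but the baseline-ADA split and the within-patient material remain.
- **SAP 16.1 contradicts SAP 16.2.** Under 16.2 a patient with pre-existing, unboosted ADA is ADA-negative, and 16.1 does not say whether that patient's positive samples count. The wording is unclear; a conflict is not shown.
- **The immunogenicity objective or the immune-tolerance provision depends on this table.** The objective's endpoints are ADA occurrence, titer, IgG subclass and neutralising antibodies. The provision in Protocol 7.4.6 is a decision for an individual patient during the study, whereas the SAP's analyses run after the last patient completes.

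**Conclusion.** The point holds as an inexpensive improvement to a descriptive analysis. The ever/never label counts PK from before seroconversion, or after a transient response, as ADA-positive. In extension-only data this has no effect if all positive patients have converted by Week 38 and stay positive. In pooled SOBI003-001 and SOBI003-002 data it affects any patient without pre-existing ADA who converts, if the pooled PK is summarised by this label. Under an assumed true ratio of 0.50, the displayed ratio would be 0.50 to 0.84 for the extension weeks and 0.57 to 0.87 with Week 1 added. These figures rest on assumed timing, equal pre-conversion exposure and pooling over occasions.

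The HS omission does not depend on timing. The protocol promises that the ADA effect on HS will be explored, and the SAP provides no output for it.

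**What to change.** In SAP 16.1:

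- Replace or supplement the ever/never split by assigning each PK value the ADA status and titer, and the neutralising-antibody result where available, of the sample at that visit.
- Where no ADA sample was taken, such as Weeks 4 and 8 after a dose adjustment, use the nearest previous one, as SAP 16.2 does for adverse events, and show the interval between the two samples.
- State that the treatment-induced and treatment-boosted definitions of SAP 16.2 apply.
- Add a within-patient plot of dose-normalised exposure against concurrent titer, so that each patient's pre-conversion values serve as reference.

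In SAP 16.2, restore PD beside PK and add the same descriptive display for HS in CSF, serum and urine, with the same rule where HS has no ADA sample at that visit.

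The cost is SAP wording and a few tables and figures from samples already planned. The drawback is small cells with 9-12 patients, so the output stays descriptive.

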16.2 Immunogenicity

The analysis of immunogenicity will in general be based on the immunogenicity analysis set. However, exceptions are the analyses of PK by ADA status at baseline, which will be based on the PK analysis set, and the AE analysis with ADA-categorized AEs in section 15.2.1.

For immunogenicity, baseline ADA (pre-existing ADA) from the previous study will be used.

The following definitions will apply as defined in the harmonised terminology for immunogenicity (Shankar et al., 2014, “Assessment and Reporting of the Clinical Immunogenicity of Therapeutic Proteins and Peptides—Harmonized Terminology and Tactical Recommendations”, The AAPS Journal, DoI:10.1208/s12248-014-9599-2):

- Evaluable patient: A patients with at least one sample taken after IMP administration that is appropriate for ADA testing (with reportable result).
- ADA-positive sample: When ADA is detected in a sample, the sample is considered positive.
- Baseline ADA: pre-existing antibodies detected at baseline.
- Treatment induced ADA: de novo development following administration of IMP (i.e., formation of ADA any time after the initial IMP administration in a patient without pre-existing ADA).
- Treatment boosted ADA: Baseline ADA boosted to higher level following IMP administration (i.e., at any time after the initial IMP administration the ADA titer is greater than the baseline titer by a factor of four).
- ADA-positive patient: A patient with at least one treatment-induced or treatment-boostered ADA-positive sample at any time during the treatment or follow-up observation period.
- ADA-negative patient: A patient without a treatment induced or treatment-boostered ADA-positive sample during the treatment or follow-up observation period.
- Baseline ADA Positive Patient: Patient with ADA at baseline. Such patient can have treatment boostered ADA after dosing.

Note that the requirement for inclusion in the immunogenicity set of at least one post-dose ADA assessment means that all patients in the immunogenicity set are “evaluable patients”.

The immunogenicity data will be listed for each patient and individual patient plots of titer measurement over time presented. Titer measurements will be summarized by visit and time point using descriptive statistics by IMP dose and overall. Immunogenicity will be evaluated in regards antibody prevalence (pre-existing antibodies), antibody incidence, titer and boosting following dosing, impact on pharmacokinetics responses.

A summary of ADA positive patients over time will be presented. For each time-point this will summarize the number of patients who were ADA positive (treatment induced or treatment boosted ADA). A summary of ADA change from baseline immune response will be presented, summarizing the overall ADA incidence (number of ADA positive patients) as well as the numbers of patients for whom this was treatment induced ADA and treatment boosted ADA, together with summaries of titer.

For the summary of treatment emergent AEs according to system organ class, preferred term and ADA-status, refer to section 15.2.1.

Figures for each patient will be produced with titer and AEs plotted against time with ADA status (positive, negative, boosted) will be marked as well.

The interval $[0 \text{ TiterMax}]$ that bounds the Titer values will be partitioned into up to four equal length intervals, where TiterMax is the maximal observed titer value. For each patient, each AE belonging to that patient will be classified according to which subinterval the nearest, previous titer belongs to when the AE occurred. For each titer-subinterval an AE summary for the SAF will be produced according to the analysis in 15.2.1 but without ADA-status. If one or more of the four subintervals are empty of corresponding AEs, then only three intervals will be used. If one or more subintervals of those three intervals are empty of corresponding AEs, only two subintervals will be used.

The same analysis will be performed for logged titers, where the interval $[0 \log(\text{TiterMax})]$ that bounds the $\log(\text{Titer})$ values will similarly be partitioned into up to four equal lengths intervals, where $\log(\text{TiterMax})$ is the maximal observed titer value.

17 The primary analysis for the pivotal phase 3 study

In the Phase III study, patients up to 30 months are planned to be included. Therefore a subpopulation of the FAS patients who are up to 30 months of age and in the FIH study was initially assigned a dose at least as high as the dose selected for the phase III study will be included in the primary analysis population for demonstrating efficacy using combined data from the FIH study and the extension study, the Phase III trial and the corresponding patients in the NH study (control patients), consisting of the 5 patients with a rapid progressive MPS IIIA disease and a baseline age of 12 to 30 months. The primary analysis methods for DQ and HS and the estimand for the pivotal phase 3 study is planned to be identical to the corresponding analysis and estimand as described in the present SAP.

18 **References**

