8.4 Immunogenicity analysis set

The immunogenicity set will consist of those patients in the safety set who have sufficient blood samples taken for ADA testing at baseline (screening visit) and at least one post-dose time-point.

For each patient in the study, all the associated safety and efficacy data in the SOBI003-001 study will be pooled and presented together with the SOBI003-002 study.

The immunogenicity set will be used for the immunogenicity analyses.

9 General issues for statistical analysis

All statistical tests will be two-sided and performed using a 5 % significance level, if not stated otherwise. Results will be presented as the estimated mean value for each treatment group, the estimated difference between groups, the associated 95 % two-sided confidence interval and P-value. P-values from statistical analyses will be presented to three decimal places with values below 0.001 displayed as <0.001 and confidence intervals will be presented to one more decimal places than the raw data.

Continuous data will be summarized using descriptive statistics: n, mean, standard deviation (SD), standard error of the mean (SE), median, minimum and maximum, unless otherwise indicated. Minimum and maximum will be presented to the same number of decimal places as the raw data and mean, standard deviation, standard error of the mean and median will be presented to one more decimal place than the raw data.

Categorical data will be summarized using counts and percentages. Percentages will be suppressed when the count is zero, however the category will still be displayed. The denominator for all percentages will be the number of patients within the treatment group for the population of interest, unless otherwise indicated. Percentages will be presented to one decimal place.

All data will be tabulated in individual patient data listings.

Statistical analyses will be performed using SAS software (SAS Institute Inc, Cary, North Carolina, United States).

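### SAP 16.2 chooses the number of titer intervals from where the adverse events fell, so an event-free titer range can vanish from the AE-by-titer tables

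*SAP*

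**What the plan says.** SAP 16.2 plans tables of adverse events by ADA titer. The range from zero to the maximum observed titer "will be partitioned into up to four equal length intervals". Events are allocated by the last titer before onset: "each AE belonging to that patient will be classified according to which subinterval the nearest, previous titer belongs to when the AE occurred". The content of each table is given as "For each titer-subinterval an AE summary for the SAF will be produced according to the analysis in 15.2.1 but without ADA-status".

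Two sentences then change the intervals after the events have been counted. The first is "If one or more of the four subintervals are empty of corresponding AEs, then only three intervals will be used". The second is "If one or more subintervals of those three intervals are empty of corresponding AEs, only two subintervals will be used". No step goes below two. The log-scale version follows the same scheme: "The same analysis will be performed for logged titers".

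No count of patients or follow-up time per titer interval is specified. The general default in SAP Section 9 is "The denominator for all percentages will be the number of patients within the treatment group for the population of interest, unless otherwise indicated". Nothing says that the finer table will be shown once it has been replaced.

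Two related displays do not use these intervals: the figures in the same section ("Figures for each patient will be produced with titer and AEs plotted against time with ADA status") and the table of treatment-emergent events by ADA status in SAP 15.2.1.

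**The concern.** The trigger for redrawing is a zero event count. It is not the absence of titers, patients or follow-up in the interval. Event counts are the outcome, and titer intervals are the exposure categories. Letting the first define the second means that the layout of the table is partly a result of what it is meant to show.

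A titer range in which patients were followed and had no events is evidence on the relation between antibodies and safety. The rule treats it as a formatting problem and widens the intervals. Events at middle titers may then be reported in the highest interval, and a gap or a step in the relation can disappear.

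This matters because safety is the primary objective. Protocol 7.5.4.3 commits to exploring how ADAs affect safety and tolerability, and Protocol 5.2 gives prominence to hypersensitivity and immune-mediated reactions.

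**Working it through.** The plan states no figure for these tables, so there is none to reproduce. The check applies the rule as written.

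**Inputs from the documents**
- Intervals: four, then three, then two, equal in length, each step triggered by an interval with no events (SAP 16.2).
- Patients: 9 to 12 planned (Protocol synopsis); 9 in the power statement (SAP 7.1).
- Scheduled serum ADA samples in the extension: Weeks 38, 52, 78 and 104, plus early termination and dose adjustments (Protocol 7.5.4.3).

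The documents contain no titer or event data. All patterns below are assumptions.

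**Step 1. What must happen when the top quarter is event-free**

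Suppose there are no events above 75% of the maximum titer and at least one between 50% and 75%. The four-interval table is discarded. Two cases remain.
- All three thirds contain an event. The three-interval table is kept, and its top row (above 66.7%) contains an event.
- At least one third is empty. Two intervals are used. The top half holds every event from the third quarter.

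Either way the final top row contains an event. Under these conditions the event-free top quarter cannot be displayed as event-free. This needs only that the same boundary convention is used for each partition.

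**Step 2. Assumed illustrations, maximum titer set to 1,000**

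| Pattern (events at titer) | Quarters | Thirds | Halves | Table kept |
|---|---|---|---|---|
| A: 20 at 50, 6 at 300, 4 at 900 | 20/6/0/4 | 26/0/4 | 26/4 | two intervals |
| B: 20 at 50, 6 at 300, 3 at 600, 2 at 700 | 20/6/5/0 | 26/3/2 | 26/5 | three intervals |
| C: 20 at 50, 6 at 300 | 20/6/0/0 | 26/0/0 | 26/0 | two intervals |

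In A the empty range from 500 to 750 disappears. In B the event-free range from 750 to 1,000 becomes part of a top third with 2 events. In C the upper half is still shown as 0, because merging stops at two; only the finer detail is lost.

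**Step 3. How often a redraw would occur with no titer effect**

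Assume a constant event rate r per person-week and independent events. An interval with m expected events is empty with probability exp(−m):
- m = 1: 37%
- m = 2: 14%
- m = 3: 5%

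With w person-weeks in each quarter, the chance that four intervals are abandoned is 1 − Π(1 − exp(−r·w)). Both assumed splits total 940 person-weeks, close to 9 patients × 104 weeks = 936.

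For 700/150/60/30 person-weeks and r = 0.02, the expected counts are 14, 3, 1.2 and 0.6. The product is 1.000 × 0.950 × 0.699 × 0.451 = 0.300, so the chance is 70%.

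| Person-weeks by quarter | r = 0.02 | r = 0.05 | r = 0.1 |
|---|---|---|---|
| 700/150/60/30 | 70% | 26% | 5% |
| 850/60/20/10 | 96% | 76% | 46% |

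The result depends strongly on how much follow-up lies at high titers, which is unknown at the planning stage.

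**Step 4. What the remaining table can tell a reader**

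A three-interval table implies that at least one quarter had no events, but not which one. It also does not show whether that quarter had patients under follow-up or no titers at all. With no patients or time at risk per interval, these two explanations cannot be separated.

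**The case against.** The strongest reply is that little depends on this. The rule is prespecified, the tables are descriptive, and no test, endpoint or decision is tied to them. With 9 to 12 patients, the individual figures of titer and events over time show any event-free period at high titer directly. The AE table by ADA status gives a second view, and the log-scale version spreads skewed titers more evenly. A zero in the top interval may also mean little: if the maximum titer comes from the Week 104 sample, hardly any follow-up remains, since AE recording ends on Day 8 of that week (Protocol 7.5.4.1.2).

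Most of this stands. It confines the harm to one summary display and rules out any claim about type I error. It does not defend the rule. The log-scale version is described as the same analysis, so it carries the same trigger. The point about thin follow-up is a reason to print follow-up time beside the zero; merging the zero away does not address it.

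Two stronger readings are tempting, and the documents support neither.
- A reader might infer that every event-free range is lost and a safe range hidden altogether. Merging stops at two intervals, so an event-free half stays visible, and the other displays keep the information.
- A reader might infer that titers from a dilution series make some interval impossible to fill, so that four intervals could never survive. The documents give neither the dilution scheme nor which end of an interval is closed, and the answer depends on both.

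**Conclusion.** The concern holds as a minor point of presentation. The titer categories in the AE-by-titer tables depend on the event counts. When the top quarter is event-free and the quarter below is not, the final top row must contain an event. That conclusion follows from the rule alone. The counts in the illustrations and the redraw probabilities of 5% to 96% rest on assumed titers, follow-up splits, flat rates and independent events; they show that redraws are plausible, not how often they will occur here. The per-patient figures and the table by ADA status are unaffected, as are the efficacy tests.

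**What to change.** In SAP 16.2:
- Set the cut points without reference to events. Either keep the four equal-length intervals on the log-titer scale or name titer steps in advance. The first still depends on the observed maximum titer, but not on the outcome.
- State which end of each interval is closed, and where ADA-negative samples go, since zero has no logarithm.
- Delete the two merging sentences, for both the raw and the log version.
- Show intervals without events as 0, with the number of patients and the follow-up time in each. A range with exposure and no events can then be told apart from a range in which no titer was observed. Patient counts alone would not do this where follow-up is short.

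The cost is a short wording change and fewer table variants to program, offset by deriving follow-up time per interval. The drawback is that some rows will be sparse or empty, which in a study of this size is accurate information.
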